Background: Recurrent transcranial magnetic stimulation (rTMS) is a consolidated procedure for the treatment of depression, with several meta-analyses demonstrating its efficacy. The theta burst stimulation (TBS) method is a modification of the usual rTMS protocol, with short bursts of stimulation at high frequencies, with the bursts themselves being applied 5 times per second. As a new intervention method, there are still few studies evaluating its efficacy in treatment of major depression. However, a recently published meta-analysis has pointed to benefits of this therapeutic modality. To date, there are no studies published with this method for the treatment of geriatric depression.

Methods/design: The proposed study is designed as a double-blind clinical trial to assess the efficacy of rTMS theta-burst in the treatment of major depressive disorder in the elderly, in a sample of 108 individuals. Patients will be randomized to two groups: the experimental (TBS) and comparative (sham) group. Inclusion criteria include a diagnosis of Major Depressive Episode and a minimum age of 60 years. The coil will be positioned in the dorsolateral prefrontal cortex, with intermittent TBS mode on the left and continuous TBS on the right. There will be 20 consecutive sessions. Outcome measures will be at eight occasions: before the intervention (baseline) and after 1, 2, 4, 6, 8 and 12 weeks of onset. The main clinical result will be measured using the Hamilton Depression Scale (HDRS), comparing the initial scores with those obtained at the end of 6 weeks after the intervention. As secondary outcomes, we will use the Global Clinical Impression Scale (CGI), the CIRS (Cumulative Disease Assessment Scale), the Geriatric Depression Scale (GDS), the intermediate scores obtained on the HDRS scale and the variations in serum BDNF concentrations. As parameters of tolerability and safety, the incidence of adverse events and the occurrence of manic and / or hypomanic symptoms will also be assessed by the Young Mania Scale (YMRS).

EXPECTED RESULTS: TBS stimulation will prove to be a safe, well-tolerated and effective intervention for the treatment of major depression in the elderly, becoming a more therapeutic option, particularly useful for patients with poor response or contraindications to the use of antidepressants.

Trial registration: NCT0484292 Registered on <https://clinicaltrials.gov/ct2/show/NCT04842929>

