The main outcome will be measured using the HDRS scale. The primary evaluation will be done at the end of 6 weeks from the start of the first day of TBS. As secondary outcomes we will use the GDS (Geriatric Depression Scale), Cumulative Illness Rating Scale (CIRS), the global clinical impression scale (CGI), Positive and Negative Affect Scale (PANAS), Montgomery-Asberg Depression Rating Scale (MADRS), and Edinburgh Handedness Inventory (EHI). All scales have already been translated and validated into Portuguese⁴⁰. Outcomes will be measured on 7 occasions: baseline after 1, 2, 4, 6, 8 and 12 weeks of study entry. The presence of adverse effects and the Young mania (YMRS) questionnaire will also be evaluated to detect manic and / or hypomanic cycling.

Cognitive Assessments

The cognitive battery will be applied by experienced neuropsychologists. For cognitive assessments they will be exploratory, secondary outcomes will be measured on the baseline, on the 20th day of the session and the addenbrooke cognitive examination will also be reapplied on the 12th week. We will use the Addenbrooke's Cognitive Examination - Revised Version (ACE-R), Ravlt - Word List, Rey's complex figure, Stroop Test (violet version); Wais III - Subtest Codes; Trail Making A and B and WASI - Vocabulary and Matrix Reasoning subtest.

Biomarkers

BDNF (brain-derived neurotrophic factor) is implicated in the pathophysiology of depression. Recent meta-analyses have shown that depressed patients have lower serum levels of BDNF than normal subjects^{41,42}. The samples will be collected in dry tubes, centrifuged within two hours after collection, then separate the serum and refrigerate it in eppendorfs at -70oC in liquid nitrogen. The samples will therefore be stored in a cryogenic bank. They will be collected at the beginning of the study and in the 6th week.

Cerebrospinal fluid (CSF) samples will be collected by means of a lumbar puncture during the evaluation procedures before the intervention begins. They will be used for the investigation of beta-amyloid peptide (Aβ1-42) and Tau protein (total and phosphorylated). These determinations will allow

the analysis of the interaction between the presence of Alzheimer's disease pathology and the therapeutic response to the TBS intervention.

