Actigraphy consists of a wrist device equipped with an accelerometer, a microprocessor and an internal memory, which are capable of detecting and storing the movement record. It is used in the evaluation of sleep disorders such as diseases of circadian rhythm, insomnia and excessive daytime sleepiness. We will use the actigraphy on the left wrist of the volunteers 1 week before the beginning of the research and for another 4 weeks after the study. The objective is to assess sleep changes associated with the clinical response to magnetic stimulation.

Pupil Examination (PLR) the participant will do a test lasting about 20 minutes in which a camera phone will record the size of your pupil during this period while you will hear some sounds. The exam is painless and without side effects.

Sample size calculation:

Based on the clinical trial of Li⁴³, which demonstrated an efficacy favoring bilateral TBS in depression of 52.5% for the active group and 17.4% for the sham group, for a two-tailed p 0.05 and a power of 90%, the total sample size is 86 subjects. Considering a rate of friction of approximately 25%, we estimated the final sample size in 108 patients.

Statistical analysis

Statistical analysis will be performed with the Stata 16 SE program for Mac OS X. All analyzes will be made on the intention to treat principle (ie the data of all participants will be included in the analysis) in which lost data will be allocated according to the last observation carried forward principle and/or mixed data. Analyzes will be considered significant at p <0.05. We will use parametric tests to analyze the main outcomes, which are allowed by the sample size. Number of previous admissions, presence of clinical comorbidities, refractoriness (measured by the Massachusetts General Hospital scale - MGH-S)⁴⁴ will be analyzed as ordinal data. For the main outcome we will use a repeated measures analysis, having HDRS scores as Dependent variable and TBS as independent variable at week 8. Secondary analyses of the other scales and biomarkers will be performed in the same way, replacing HDRS as a dependent variable.

Study Flow Chart

We show below the flowchart for each patient throughout the study. It is worth remembering that TBS will be applied 23 times: 20 consecutive sessions (week 0 through week 4), 6th week, 8th week and 12th week. Still, patients who receive *sham* stimulation and who are still depressed may receive active stimulation at the end of the study.

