Table 1. Study schedule

	Triage	Baseline	Week						
			1	2	3	4	6	8	12
Assessment of eligibility	X								
Structured interview (MINI)	X								
Consent form	X								
Theta-burst stimulation (active/sham)			D	D	D	D	W	W	W
Clinical interviews	X		X	X		X	X	X	X
Adverse effects			X	X		X	X	X	X
Blood collection for serum biomarkers		X					X		
Neuropsychological evaluation		X					X		X
Cerebrospinal fluid collection		X							

“D” and “W” represent interventions performed daily and weekly, respectively.

Ethical aspects and safety

The rTMS is very safe when used properly and has few adverse effects, and as mentioned above, the most common is headache. Applications will always be made in a hospital setting with a physician present. We will evaluate patients 23 times over 12 weeks - so that we can quickly identify any worsening of the clinical picture and perform early intervention.

The study is approved by the Research Ethics Committee (CAAE: 80215117.5.0000.0068). All enrolled subjects will consent to participate through an Informed Consent Form. All the procedures described present minimal risk. If a volunteer presents a risk of major suicide, the same will be excluded from the study, adopting the standard procedure for the management of this type of patient. Participants may have access to their data and may leave the study at any time, without prejudice to any treatment they may perform within the institution. The data will be collected, analyzed and published in order to preserve the anonymity of the individual. In addition, the study will be conducted in accordance with all requirements of the Research Ethics Committee and also based on the recommendations established in the Declaration of Helsinki (1964), as amended in Tokyo (1975), Venice (1983) and Hong Kong (1989). As a benefit, participants will be able to participate in a clinical trial to treat their clinical condition. This

will be possible even if they receive sham stimulation, as they may receive active stimulation at the end of the study if they still have severe depressive symptoms.

Discussion

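### The main model's week 8 conflicts with the week-6 primary evaluation, and the secondary-analysis rule makes pre-treatment CSF an outcome, so the stated CSF interaction has no model

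*Combined protocol and SAP*

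**What the plan says.** **Main model.** The Statistical analysis section plans a repeated-measures analysis "having HDRS scores as Dependent variable and TBS as independent variable at week 8". The next sentence extends it: "Secondary analyses of the other scales and biomarkers will be performed in the same way, replacing HDRS as a dependent variable".

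**Primary time point.** Clinical variables: "The primary evaluation will be done at the end of 6 weeks from the start of the first day of TBS". The abstract describes the main result as "comparing the initial scores with those obtained at the end of 6 weeks after the intervention".

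**CSF.** Under Biomarkers, CSF "samples will be collected by means of a lumbar puncture during the evaluation procedures before the intervention begins". The analytes are beta-amyloid 1-42, total tau and phosphorylated tau. The stated purpose is to analyse the interaction between the presence of Alzheimer's disease "pathology and the therapeutic response to the TBS intervention". In Table 1 the row "Cerebrospinal fluid collection" has one mark, at Baseline. No section gives a model with HDRS as outcome and a CSF term, a choice among the three analytes, a cut-off, or a definition of when pathology is present. The Discussion says only that the data could help in analysing some predictors of response.

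**Cognition.** Cognitive Assessments sets testing at baseline and at the 20th session, with the ACE-R repeated at week 12. Table 1 marks neuropsychological evaluation at Baseline, week 6 and week 12.

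**The concern.** The primary comparison should rest on one time point named in advance. Here the section defining the outcome and the section defining the model name different weeks. A further stimulation day is scheduled in week 6 and another in week 8, so the two visits also follow different exposure.

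The CSF problem is one of direction. The aim is effect modification: does the HDRS response to TBS differ by Alzheimer's pathology? That needs HDRS on the left of the model and CSF on the right. The written rule puts CSF on the left. Followed literally, a lumbar puncture yields an analysis that cannot answer the question given for it. If an interaction is fitted instead, the marker and its coding can be picked after the results are known.

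**Working it through.** **1. Time point, side by side.**

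| Place | HDRS time point |
|---|---|
| Abstract | 6 weeks |
| Clinical variables | 6 weeks from the first TBS day |
| Statistical analysis | week 8 |

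Both visits exist in Table 1, so either analysis could be run. The documents give no HDRS standard deviation or between-visit correlation, so the effect on the estimate cannot be computed. The error rate can be bounded. For two two-sided tests at 0.05 with the better one reported, the chance of at least one false positive lies between 5% (perfectly correlated) and 1 − 0.95² = 9.75% (independent).

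**2. What the literal rule estimates for CSF.**

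- CSF values per participant: 1 before treatment, 0 after.
- Literal model: CSF = a + b·TBS. Allocation is randomised and the sample precedes treatment, so the expected value of b is 0 whatever TBS does. There is no repeated measure either.
- Model for the stated aim: HDRS at follow-up = a + b1·(baseline HDRS) + b2·TBS + b3·marker + b4·(TBS × marker). The target is b4, and no term of the literal model corresponds to it.

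This follows from the sampling schedule alone.

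**3. What stays open if the Biomarkers section overrides the rule.** Three analytes × two codings (continuous or cut) = 6 specifications at one HDRS time point. Six independent tests would give 1 − 0.95⁶ = 26.5%. These tests are correlated, so the figure was simulated with no true interaction.

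- Trial size: 86, the plan's number before attrition. It reproduces from 52.5% versus 17.4%, two-sided 0.05, 90% power. The pooled formula gives [1.960·√(2 × 0.3495 × 0.6505) + 1.282·√(0.525 × 0.475 + 0.174 × 0.826)]² / 0.351² = 36.66 per arm. The continuity correction gives (36.66/4)·[1 + √(1 + 4/(36.66 × 0.351))]² = 42.2, so 43 per arm and 86 in total.
- Model: least squares with treatment, baseline HDRS, marker and interaction; 4,000 trials per setting.
- Assumed, not in the documents: correlation between markers 0, 0.5 or 0.8; cut at 30% positive; CSF available for everyone.

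Result: at least one of six p-values below 0.05 in 17.5% to 21.9% of trials, against 4.3% to 5.1% for a single fixed model.

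**4. Cognitive schedule.** Twenty weekday sessions take about four weeks, so the 20th session falls near week 4; Table 1 puts that assessment at week 6. The table column appears to be read correctly: the blood row has its follow-up mark in the same column, and the Biomarkers text separately gives week 6 for blood. Both places support a week-12 assessment. The text limits it to the ACE-R; the table does not.

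**The case against.** The best defence is that the specific governs the general. CSF is in neither list of secondary outcomes: the abstract names only serum BDNF as a biomarker, and Clinical variables lists scales. Biomarkers gives CSF a purpose of its own, and a repeated-measures analysis of something measured once cannot be run as such. This is a fair reading. It narrows the CSF fault from a wrong model to a missing one, but does not remove it: on either reading the stated interaction has no analysis.

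On timing, week 8 may mean data through week 8. Even so, week 6 is not named as the contrast that decides the trial.

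Three stronger readings are tempting, and the documents do not support them.

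- A reader might infer that the quoted sentence undermines the primary HDRS result. It governs secondary analyses only; the time-point conflict arises in the sentence before it.
- A reader might count twelve CSF specifications by including two HDRS time points. The time point is a separate fault with its own remedy, so it should not be counted again here.
- A reader might infer that the week-8 reference gives free choice for BDNF and the pain tests, which have no week-8 value. Each has one post-baseline value (week 6 and week 4), so this is loose wording that changes no result.

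**Conclusion.** Both parts hold. The time-point conflict is the more important because it touches the primary analysis. It rests on the text alone, and its error-rate cost is at most 9.75% instead of 5%, and only if the choice follows sight of the results.

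The CSF fault also rests on the text alone, but is confined to an exploratory analysis and does not alter the primary conclusion. The 18% to 22% figure is an upper case: it requires that all six specifications be tried and the best reported, under the assumed correlations and cut. The plan announces no confirmatory CSF claim.

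A reader might also infer that the interaction model would recover the full effect of true pathology. It would not if CSF measures pathology with error. With an assumed 30% prevalence, a continuous marker equal to pathology plus noise has an expected interaction slope of 0.21/(0.21 + noise variance) times the true one, where 0.21 = 0.3 × 0.7. For noise standard deviations of 0.25, 0.5 and 1.0 that is 0.77, 0.46 and 0.17. The model asks the right question; it does not guarantee a precise or undiluted answer.

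**What to change.** Before unblinding:

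1. Reconcile the abstract, Clinical variables and Statistical analysis to one primary HDRS time point, and use it for the secondary scales.
2. Exclude CSF from the rule that replaces HDRS as the outcome. Keep HDRS as outcome and add marker and treatment-by-marker terms, in either the planned repeated-measures model or a baseline-adjusted model at the primary time point.
3. Name the marker (beta-amyloid 1-42, total tau, phosphorylated tau or a stated combination), say whether it is continuous or cut, and give any cut value. Report the interaction as an exploratory estimate with a confidence interval.
4. Reconcile the cognitive schedule between Cognitive Assessments and Table 1, retaining the week-12 ACE-R, and state which visits are analysed.
5. Add a clause that BDNF is analysed at week 6 and the pain tests at week 4, each accounting for baseline. This is for clarity only.

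The cost is wording in the analysis plan and one schedule reconciliation. No new samples or visits are needed.

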Here we provided the study protocol of a randomized controlled trial (RCT) that will evaluate the efficacy of TBS for the treatment of geriatric depression. To the best of our knowledge, this is the first study in this field. The participants will receive 23 sessions of bilateral TBS, comprising first inhibitory stimulation delivered by cTBS in the right DLPFC followed by excitatory stimulation delivered by iTBS in the left DLPFC, totalizing 3600 pulses. We performed sample size calculation based on the effect size found in the most similar clinical trial found in literature⁴⁵. There are no specific treatments using neuromodulation for depression in the elderly. This study aims to answer this question. We will enroll patients with different degrees of refractoriness and the TBS as the only treatment for depression (the antidepressants will be wash-out). , which will significantly increase the external validity of our results. These data could contribute to the analysis of some predictors of response as well.

We expect that TBS will be statistically superior to sham treatment for depression as assessed through the Hamilton Depression Rating Scale (HDRS). Other expected secondary outcomes consist of: TBS will be superior to sham treatment for improvement of depressive symptoms by the GDS (Geriatric Depression Scale), the MADRS (Montgomery-Asberg Depression Rating Scale), and the Global Clinical Impression Print Scale (CGI). Regarding serum markers, we expect that the TBS group active vs. sham will show a significant increase in BDNF levels. From the neurocognitive point of view, we expect that both groups will perform similarly.

Conclusions

This study will investigate the efficacy of TBS for the treatment of major depressive disorder in elderly patients using a randomized, sham-controlled design. The biomarker investigation will contribute to the understanding of the neurobiological mechanisms of depression and their relationship with the treatment. This trial will contribute valuable information to the treatment of depression in the elderly.

Author's contributions:

LV is responsible for initiating and managing the trial, conceived and designed the essay, analyse the data and wrote the manuscript. PJCS, WG, AB, OF performed the statistical analyzes, LS, RB, CM, JL are responsible for the clinical evaluation.LT, HC, RV, RM responsible for the neuropsychological evaluation. PO responsible for the collection of CSF, KM responsible for collecting

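### The abstract and methods give different secondary outcome lists, and every secondary outcome is tested at p<0.05 with no ranking or error control

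*Combined protocol and SAP*

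**What the plan says.** The abstract (Methods/design) names CGI, CIRS and GDS as secondary outcomes, together with "the intermediate scores obtained on the HDRS scale and the variations in serum BDNF concentrations". Under Clinical variables the secondary outcomes are GDS, CIRS and CGI, followed by "Positive and Negative Affect Scale (PANAS), Montgomery-Asberg Depression Rating Scale (MADRS), and Edinburgh Handedness Inventory (EHI"). BDNF is described separately under Biomarkers.

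The Statistical analysis section sets one threshold: "Analyzes will be considered significant at p <0.05". After describing the HDRS analysis it adds: "Secondary analyses of the other scales and biomarkers will be performed in the same way, replacing HDRS as a dependent variable". It gives no ranking, testing order, adjustment or limit on claims. Only the cognitive tests are called exploratory, in a sentence that also uses the word secondary. Cortical excitability, sensory thresholds, pain modulation, actigraphy and pupil testing have no stated place in the hierarchy.

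The Discussion says what the investigators hope to claim: "Other expected secondary outcomes consist of: TBS will be superior to sham treatment for improvement of depressive symptoms by the GDS (Geriatric Depression Scale"), and likewise by MADRS and CGI. It also expects a significant BDNF increase with active treatment. For cognition it expects no difference between groups.

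**The concern.** Both the abstract and Clinical variables present their lists as the secondary outcomes, yet the lists do not match. Within these documents, nothing says which one governs reporting. Because each outcome faces an unadjusted 0.05 test, a statement such as superiority on MADRS or a significant BDNF rise would carry no control of the overall error rate. A reader of the results could not tell from this plan whether that outcome had been singled out in advance.

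The time point adds a further choice. Analysing secondary outcomes like HDRS means inheriting week 8 from the Statistical analysis section, whereas the abstract and Clinical variables place the primary evaluation at week 6. BDNF is drawn only at the start and at week 6, so a week 8 analysis cannot be applied to it.

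**Working it through.** **1. The lists side by side**

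| Outcome | Abstract | Clinical variables | Discussion (expected results) |
|---|---|---|---|
| GDS | yes | yes | yes |
| CGI | yes | yes | yes |
| CIRS | yes | yes | no |
| Intermediate HDRS | yes | no | no |
| BDNF | yes | no (own Biomarkers section) | yes |
| MADRS | no | yes | yes |
| PANAS | no | yes | no |
| EHI | no | yes | no |
| **Count** | **5** | **6** | **4** |

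The union holds 8 outcomes, counting intermediate HDRS once. Only GDS and CGI are in all three columns.

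**2. The plan's own figure**

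The documents state no family-wise error rate. Their one related calculation is the sample size: "for a two-tailed p 0.05 and a power of 90%, the total sample size is 86 subjects", from 52.5% against 17.4%. With 1:1 allocation (assumed; the ratio is not stated), the two-proportion formula gives 37 per arm (74 in total) without a continuity correction and 43 per arm with it. 2 × 43 = 86, so the figure reproduces. The two-sided 0.05 was budgeted for one comparison and makes no allowance for secondary outcomes.

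**3. Chance of at least one false positive**

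Inputs: 0.05 per test (Statistical analysis), one test per outcome, and no true effect on any outcome (both assumed here). For k independent tests the chance is 1 − 0.95^k.

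- k = 4 (Discussion): 1 − 0.95^4 = 18.5%
- k = 5 (abstract): 1 − 0.95^5 = 22.6%
- k = 6 (Clinical variables): 1 − 0.95^6 = 26.5%
- k = 8 (union): 1 − 0.95^8 = 33.7%
- k = 13: 48.7%; k = 14: 51.2%

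The union is generous. EHI measures handedness, and CIRS is also an eligibility criterion. Without both, k = 6 (26.5%). Testing intermediate HDRS at several visits, or PANAS by subscale, would raise the count.

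**4. Allowing for correlation**

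The documents give no correlations, so a range is shown. The figures come from simulating equicorrelated normal test statistics (400,000 draws, two-sided 5% critical value).

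| k | r = 0 | r = 0.3 | r = 0.5 | r = 0.7 |
|---|---|---|---|---|
| 4 | 18.5% | 17.4% | 15.7% | 12.9% |
| 6 | 26.5% | 24.2% | 20.8% | 16.5% |
| 8 | 33.7% | 29.9% | 25.0% | 19.1% |
| 14 | 51.3% | 43.8% | 34.7% | 24.9% |
| 20 | 64.1% | 54.0% | 41.9% | 29.0% |

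The r = 0 column agrees with step 3 to within simulation error.

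**5. Cost of error control**

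Holm's first step with four outcomes is 0.05/4 = 0.0125, with critical value 2.498 instead of 1.960.

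- 90% power at 0.05: 1.960 + 1.282 − 2.498 = 0.744, giving about 77%.
- 80% power at 0.05: 1.960 + 0.842 − 2.498 = 0.304, giving about 62%.

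These apply to an outcome that must pass at the first step, before the condition that the primary test succeeds. Later Holm steps are less strict.

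**The case against.** The strongest reply is that this is an incomplete abstract rather than a set of competing lists. The Discussion states expectations and does not define outcomes. BDNF is absent from the Clinical variables list because it has its own section. Intermediate HDRS is implied by the seven measurement occasions, and EHI is not a plausible efficacy outcome. On that reading the substantive discrepancy is MADRS and PANAS. This largely stands, and the formal conflict is between the abstract and Clinical variables. It does not answer the absence of ranking or error control. The Discussion still matters because it shows that significance claims are intended.

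A reader might infer that a chance significant secondary result is likely, meaning more probable than not. The documents do not support that. The listed outcomes give 19% to 34% under independence, and less for depression scales that measure much the same illness. Passing 50% takes at least 14 roughly independent tests, hence the cognitive or physiological measures. The cognitive tests are called exploratory with no difference expected, and the stated aim of actigraphy is to relate sleep changes to clinical response. The general 0.05 rule does reach these measures, but no superiority claim on them is announced.

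A reader might also infer that the reported list will be picked after the results are known. The trial is registered and the registration is not available here; it may fix the list. The point is limited to what these documents settle.

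Finally, the calculation supposes no true effect anywhere, and secondary testing leaves the error rate of the single primary outcome untouched. Both are correct. Formal control of secondary outcomes is partly a matter of judgement, and labelling them supportive would be an adequate answer. The plan currently does neither.

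**Conclusion.** The concern holds in limited form. The abstract and Clinical variables disagree on the secondary outcomes, all are tested at an unadjusted 0.05, and superiority or significance is anticipated on four of them. With no true effects and one test per outcome, the chance of at least one false positive is roughly four to seven times the nominal 5% under independence (18.5/5 = 3.7; 33.7/5 = 6.7). At correlations of 0.3 to 0.7 it falls to about 13% to 30% for 4 to 8 tests. This affects the credibility of secondary claims only. It is worth correcting before unblinding, because afterwards these documents alone could not separate planned from selected results.

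**What to change.** 1. Use one secondary list in the abstract, Clinical variables, Statistical analysis and Discussion. Limit significance claims to the four outcomes with a stated hypothesis: MADRS, GDS, CGI and BDNF.
2. Reconcile the primary time point first (week 6 in the abstract and Clinical variables, week 8 in Statistical analysis); until then, any rule conditional on the primary test is undefined. Then analyse MADRS, GDS and CGI at that time point, and BDNF at week 6, its only post-baseline draw.
3. Test the four by Holm at a two-sided family level of 0.05, only after a successful primary HDRS test. Alternatively, label them supportive and make no significance claim.
4. Report PANAS, CIRS, intermediate HDRS and the cognitive and physiological measures as estimates with 95% confidence intervals and no significance claim. Treat EHI as a baseline descriptor.

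The change needs protocol and SAP wording only, with no added patients, visits or assessments. The Holm option has a real price: at its first step, 90% power falls to about 77% and 80% to about 62%. The supportive label avoids that price by giving up the significance claims.
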